- Patients without regular internet access through a computer, tablet or smartphone are excluded.
- Subjects requiring long-term inpatient nursing care are excluded. For patients enrolled as inpatients, individuals being discharged to both home and acute rehab are eligible. Individuals being discharged to a skilled nursing facility or hospice are excluded.
- Expected life expectancy less than 6 months or other inability to comply with study follow-up.
- Pregnant women and prisoners are excluded

Vulnerable populations: Children, pregnant women, fetuses, neonates, and prisoners are not included in this research study.

Sample Size: 20 subjects will be enrolled.

Accrual: The comprehensive stroke center at the Hospital of the University of Pennsylvania (HUP) is a tertiary referral center for acute ischemic stroke, with annual case volumes of approximately 600 strokes per year on the inpatient stroke service. Additionally, the stroke team sees patients in the outpatient clinic both in follow-up from their acute hospitalization and in consultation to provide second opinions for patients treated elsewhere. Due to the broad inclusion criteria of this study, it is expected that many of the patients seen, both inpatient and outpatient, will be eligible for participation in this study. We expect that we will be able to enroll 1-2 patients per week and will complete enrollment within 6 months.

Recruitment: A stroke physician evaluates all patients with acute ischemic stroke who present to HUP. All stroke team physicians will be trained investigators in this study, and they will screen patients for eligibility during routine clinical care. Study physicians will also screen for potentially eligible subjects during outpatient clinic sessions. All eligible subjects will be informed of the study, and if they are interested in participation, a study physician will obtain informed consent. The original signed consent form will be kept in the study binder. A copy of

the signed consent form will be given to the patient and another copy will be placed in the medical record.

Procedures

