Subjects will be seen by the study team 90 days +/- 14 days after enrollment to assess their neurologic function using the NIHSS, mood using the PHQ-9, functional status using the modified Rankin Scale, Quality of life using the Euroqol EQ-5D,^{20, 21} healthcare utilization using the Stanford Health Utilization survey,²² whether any other treatment for mental health problems was received (including medication and psychotherapy) and perceived utility of Joyable iCBT for depression as well as perceived barriers to successful use of internet-based CBT.

Table 1. Study measures and timing of assessment

	Baseline	72 hr Call	30 day call	90 day visit
Demographics	X			
Stroke information	X			
SSRI Use	X		X	X
Assess for technical problems		X	X	
NIHSS	X			X
mRS	X		X	X
EQ-5D	X		X	X
SHU				X
PHQ-9	X			X
Semi-Quantitative assessment of perceptions about Internet-based CBT				X

NIHSS=National Institute of Health Stroke Scale, EQ-5D=Euro-Qol 5D, SHU=Stanford Health Utilization survey, PHQ-9=Patient Health Questionnaire 9,

Analysis Plan

The baseline demographic variables of the study population will be summarized using means, medians, and proportions as appropriate. For each subject, we will calculate the total amount of time spent interacting with the Joyable program and the total number of Joyable activities that the patient successfully completed. We will then calculate averages across the study population. These metrics will provide important information on the average “dose” of CBT received. In an exploratory analysis we will look for relationships between baseline clinical and demographic factors and number of activities completed.

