We will calculate the average PHQ-9 score at enrollment and 90 days. We will compare the PHQ-9 score from enrollment to day 90. The statistical power of this test is uncertain. In Table 2 we present estimated study power (with $\alpha=0.05$) across a range of assumptions about both the change in PHQ-9 over time and the standard deviation of the difference in PHQ-9 over time. These calculations show that although this is a small pilot study, we have >80% power to detect a difference in PHQ-9 of 3 or more points across a range of assumptions. The PHQ-9 will also be administered to subjects weekly via through the Joyable program. We will examine whether there are significant changes in score over time using repeated measures analysis (generalized estimating equations, GEE) with PHQ-9 score as the dependent variable and week as the independent variable.

In an exploratory analysis, we will divide patients into two groups based on PHQ-9 at study completion (*high depression symptoms*, defined as median or above and *low depression*

symptoms, defined as below the median score). Healthcare outcomes, including modified Rankin scale, health related quality of life, and healthcare utilization will be compared across groups. We hypothesize that patients with high depression symptoms will have worse functional outcome, lower quality of life, and higher healthcare utilization. We will also divide patients into groups based on their participation in the Joyable program and compare outcomes (e.g., PHQ-9 score, quality of life, health utilization) between subjects who showed high engagement in the program and those who showed low engagement.

Table 2. Statistical Power for single sample paired t-test

SD of the Difference	Difference in PHQ-9 Pre/Post Treatment				
	1	2	3	4	5
2	61%	99%	100%	100%	100%
3	32%	85%	99%	100%	100%
4	20%	61%	92%	99%	100%
5	15%	43%	77%	95%	99%
6	12%	32%	61%	85%	96%

Data Confidentiality

Internet-based files will only be made available to personnel involved in the study through the use of access privileges and passwords. Paper-based records will be kept in a locked, secure location and only accessible to study personnel. Prior to access to any study-related information, personnel will be required to sign statements agreeing to protect the security and confidentiality of identifiable information. Whenever feasible, identifiers will be removed from study-related information.

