No clinical information obtained by the research team will be sent to Joyable. De-identified data from Joyable will be sent to the research team, which will include the number of Joyable activities completed by the subject, the number coaching interactions, and results of Joyable administered PHQ-9 and satisfaction assessments. This data will be organized by subject identification number, which can be used to link to the data collected by the research team. The research team will maintain a password protected file on a secured computer at the University of Pennsylvania which will link subject identification number to identifying information for each subject (name, medical record number, date of birth). Access to this file at the University of Pennsylvania will be limited to the PI and the study research coordinator. A Microsoft Excel document will be created which will include subject name, date of birth, and study identifier. This document will be uploaded to Penn+Box. The study team at Joyable will be given access to the file via Penn+Box. They will use this information to link the Joyable data elements described above to each subject. Joyable will then upload a Microsoft Excel file containing this data and subject identifier to the study Penn+Box, where it will be downloaded by the research team.

Patients who enroll in the study will all be participating in Joyable's iCBT Program for Depression. During enrollment in the study, patients will create an account with Joyable. As a part of this process, subjects register with Joyable using the same process as they currently use for their commercially available program. Registration requires the subject to submit the following PHI: name, date of birth, gender, and email address. Access to PHI will be limited to those who need it. This may include the individual coach who is assigned to each subject, coach managers who have access to subject data for the coaches that report to them, Joyable's analytic team which

has access to data for the purpose of aggregating and sharing back results to the research team, and a small number of engineers who can access data in order to troubleshoot bugs in the software. Subject interactions with Joyable will be governed by Joyable's existing Privacy Policy (see <https://joyable.com/privacy>) and terms of use (see <https://joyable.com/terms>).

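### The weekly PHQ-9 GEE uses only scores that come through the app, so its slope can be biased, in either direction, if stopping the app depends on mood

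*Combined protocol and SAP*

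**What the plan says.** The Analysis Plan contains two analyses of PHQ-9 change. The first compares the enrollment score with the Day-90 score. Both are collected by the study team (Study Procedures, Baseline; 90 Day In-person Visit; Table 1), and the visit is not tied to app use: "Subjects will be seen by the study team 90 days +/- 14 days after enrollment". The power table belongs to this analysis: "Table 2. Statistical Power for single sample paired t-test".

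The second is the weekly analysis. It opens with "The PHQ-9 will also be administered to subjects weekly via through the Joyable program" and is then specified as "repeated measures analysis (generalized estimating equations, GEE) with PHQ-9 score as the dependent variable and week as the independent variable". The Data Confidentiality section confirms the route: the file that Joyable sends to the team includes "results of Joyable administered PHQ-9 and satisfaction assessments". No weights, imputation, working correlation or missing-data assumption is given for the GEE, and nothing says that the study-team scores are part of it.

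The plan also compares outcomes, PHQ-9 among them, between subjects with high and low engagement, without stating a hypothesis for that comparison.

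**The concern.** Adherence is a primary outcome and program completion a secondary one, so the trial is built around the possibility that subjects stop. A subject who stops using the app is likely to stop producing weekly scores. Later weeks then rest on those who stay, and if staying depends on mood, the fitted slope mixes true change with a change in who is being measured.

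This error is in the slope itself, so a better standard error does not remove it. A reader could take a significant weekly trend as support for Objective 2 when it partly reflects who kept using the app. The study team already holds two scores that do not depend on app use, and the weekly model as described leaves them out.

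**Working it through.** **Inputs from the plan.** Single arm, "Sample Size: 20 subjects will be enrolled"; 8-week program; entry PHQ-9 of 5 to 19; alpha 0.05; study-team PHQ-9 at baseline and Day 90 (90/7 = 12.9 weeks).

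**The plan's own figure.** None is given for the GEE. Table 2 is reproduced by power = Φ(d√20/SD − 1.96). For d = 3:
- SD 4: 3.354 − 1.96 = 1.394, giving 91.8% (plan 92%).
- SD 5: 2.683 − 1.96 = 0.723, giving 76.5% (plan 77%).
- SD 6: 2.236 − 1.96 = 0.276, giving 60.9% (plan 61%).

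All 25 cells agree within 0.8 percentage points. Table 2 therefore describes the Day-90 comparison with all 20 subjects. Its grid of 1 to 5 points gives a scale for judging the bias below.

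**Why the slope moves.** GEE solves Σ Xᵢ′Vᵢ⁻¹(Yᵢ − Xᵢβ) = 0 over the observed weeks. This is centred on the true β in general only if the subjects still observed at a week have the same mean as all subjects would have had.

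A worked case: half the subjects stay at 15 and half at 7 throughout (mean 11). The weekly stopping logit is log(0.08/0.92) + 0.2 × (score − 11).
- Score 15: −2.442 + 0.8 = −1.642, a 16.2% chance of stopping per week; 0.838⁸ = 0.243 remain at week 8.
- Score 7: −2.442 − 0.8 = −3.242, or 3.8% per week; 0.962⁸ = 0.736 remain.
- Observed week-8 mean: (0.243 × 15 + 0.736 × 7)/(0.243 + 0.736) = 9.0.

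The observed mean falls by 2.0 points although nobody changed.

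**Simulation.** n = 20, weeks 0 to 8, true change zero, mean 11. All variances and stopping rates are assumed, since the plan gives none.
- A: random intercept SD 2, AR(1) SD 3 (0.8 per week), error SD 1.5.
- B: random intercept SD 3, random slope SD 0.45 per week, error SD 2.2.
- C: random intercept SD 3.5, random slope SD 0.45 per week, error SD 2, scores kept within 0 to 27.

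In A and B stopping depends on the last score, with 8% per week at a score of 11 and 43–51% still active at week 8 (220–350 replicates). In C it depends on the current score (600 replicates).

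| Setting | Log-odds of stopping per point | Week-8 bias, independence | Week-8 bias, exchangeable |
|---|---|---|---|
| A | 0.1 / 0.2 / 0.3 | -0.50 / -0.92 / -1.44 | +0.04 to +0.35 |
| B | 0.1 / 0.2 / 0.3 | -0.93 / -1.59 / -2.48 | -0.16 to -0.73 |
| C, 30% stopped | 0.15 / 0.3 | -0.90 / -1.54 | -0.31 / -0.56 |
| C, 50% stopped | 0.15 / 0.3 | -1.64 / -2.52 | -0.51 / -0.92 |

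A further run gave about -0.4 to -2.5 (independence) and +0.5 to -0.8 (exchangeable). The overall ranges are therefore about -0.4 to -2.5 and +0.5 to -0.9.

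**Effect on the test.**
- Independence: in A and B a two-sided 5% test rejected 5–29% of the time, even with a small-sample-corrected standard error. In C, false improvement occurred in 11–43% of trials against a nominal 2.5%.
- Exchangeable: 5–14% false improvement in C.
- Control: with stopping unrelated to mood, the estimate was 0.01 to 0.08 points and false improvement 2–4%, which isolates the cause.

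**Direction.** A and B are symmetric about 11, so reversing the sign of the log-odds reverses the sign of the bias.

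**The Day-90 comparison under the same stopping (C).** Mean change 0.01 to 0.04 points and false improvement 2–3.5%, with all subjects attending.

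**Using the study-team scores.** A mixed model with random intercept and AR(1) errors that includes baseline and Day 90 left -0.13 to +0.03 in one set of runs of A and B. A less favourable set left about +0.1 to -0.5 with full attendance, and up to about -0.7 if half of the app-stoppers miss Day 90. With all 20 at Day 90, the SD of its week-8 estimate was 1.05–1.18, against 1.21–1.47 for independence GEE, so no precision was lost.

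**The case against.** The strongest reply is that Objective 2 does not depend on the weekly slope. PHQ-9 reduction is a primary outcome, Table 2 powers the enrollment-to-Day-90 comparison, and that comparison includes app-stoppers who attend. This stands. A reader might infer that the team's scores on app-stoppers go unused; they do not. They are absent only from the GEE as described.

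The plan is also silent rather than wrong on working correlation. The largest figures come from independence correlation, which it never names; under exchangeable the bias is smaller and can take either sign. This stands too, and it is why neither size nor direction can be fixed in advance.

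A reader might take the engagement comparison as an admission that the plan expects mood and app use to be related. It says only that outcomes will be compared, and it does not say that worse mood causes stopping.

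Finally, it is an inference that weekly scores end when app use ends. The documents say that the PHQ-9 is given weekly through Joyable and that coaches reach out to participants on their own initiative; they do not say that assessments cease when activities lapse. Even so, the plan names no other source of weekly scores and no rule for missing ones.

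**Conclusion.** The point holds for the supporting weekly analysis only. As described, the GEE can give a wrong week slope if stopping depends on mood: toward improvement if worse subjects stop, and the other way if subjects stop because they feel better. With no true change, the illustrative week-8 bias is about -0.4 to -2.5 points under independence correlation and about +0.5 to -0.9 under exchangeable. These figures rest on assumed stopping rates, assumed variances and permanent stopping.

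The documents do not support the stronger conclusion that the trial's main PHQ-9 result is biased by app stopping. The enrollment-to-Day-90 comparison is not affected if all subjects attend. The change is worth making because it is cheap and the scores are already collected.

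**What to change.** Replace the GEE sentence in the Analysis Plan with wording such as:

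> Weekly PHQ-9 will be analysed by a linear mixed model (REML, Kenward-Roger) with a random subject intercept and AR(1) within-subject errors, and time in weeks since enrollment with a knot at week 8. The study-team baseline and Day-90 PHQ-9 will be included for every subject who has them. The number of subjects contributing at each week will be reported. The enrollment-to-Day-90 comparison is the main test of PHQ-9 change; the weekly model is supportive. The model reduces bias from mood-related stopping but may not remove it, particularly if subjects who stop the app also miss Day 90.

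The knot keeps Day 90 from forcing a single straight line over about 13 weeks.

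Cost: analysis-plan wording only, with no new data. The downsides are one more covariance assumption and two modes of administration in one model. Examine mode by comparing app and study-team scores taken close together at enrollment, provided the first app PHQ-9 is completed then. Do not examine it by refitting without the study-team scores, because that restores the stopping bias: in setting B, an app-only random-intercept plus AR(1) fit gave -0.23 / -0.45 / -0.69 with no mode effect simulated.

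An inverse-probability-weighted GEE is not proposed. In setting B, with estimated weights and exchangeable correlation (400 replicates), it left -0.20 / -0.45 / -0.64, against -0.24 / -0.42 / -0.60 unweighted.

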Protocol Title: Internet-based Cognitive Behavioral Therapy to Reduce Depressive Symptoms after Stroke Pilot/Feasibility Study

Short Title: Internet-based CBT for Depression after Stroke Pilot

Investigators:

[name]
[name]
[name]

Brief Description:

Stroke is one of the leading causes of death and disability in the United States, with estimated direct and indirect costs exceeding 70 billion dollars per year. Depression is common after stroke, occurring in approximately 25% of all patients. Depression has been associated with lower quality of life, higher mortality, increased healthcare utilization and higher costs. Cognitive behavioral therapy (CBT) interventions have been shown, in small studies, to both treat and prevent the development of post-stroke depression. CBT based interventions therefore have the potential to improve quality of life and reduce healthcare costs after stroke. Unfortunately, there are significant barriers to the widespread use of CBT in the stroke population, including limited access to licensed providers, high costs of treatment, and limited mobility. Alternative methods for delivering CBT have the potential to improve access and reduce costs and may make widespread dissemination of CBT based treatment possible. We aim to test the feasibility of an internet-based CBT (iCBT) program combined with a telephone/email based coaching service in patients with recent stroke. We will do this by partnering with Joyable. Joyable is an existing, commercially available iCBT program. Joyable's iCBT Program for Depression combines 42 brief online activities with a telephone/email based coaching service, which is designed to motivate and encourage individuals to complete the online modules.

Objectives:

1. Determine the feasibility of internet-based CBT in patients with recent ischemic stroke and depressive symptoms, by quantifying adherence to the program in a pilot population of 20 subjects.
2. Quantify changes in depressive symptoms and quality of life in subjects pre- and post-program participation, to provide preliminary evidence of the efficacy of internet-based CBT to improve outcomes after stroke.

Primary Outcome variables

The primary outcomes will be the number of activities in the iCBT program completed by participants and reduction in depressive symptoms, measured the 9-item Patient Health Questionnaire (PHQ-9).

Secondary Outcome variables

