Secondary outcome variables will include: completion of the iCBT program, number of telephone/email based coaching interactions, quality of life, measured using the EuroQOL-5D

(EQ-5D), healthcare utilization, measured using the Stanford Health Care Utilization Survey, and subject satisfaction with the program.

Background

Depression after stroke

Depression is common after stroke, occurring in up to one-third of all stroke patients.¹ A recent American Heart Association (AHA) scientific statement on post-stroke depression highlighted the importance of this condition, noting that it was “under-recognized, under-investigated, and under-treated.”² Individuals with depression after stroke have been shown to have lower functional status and lower quality of life than those without depression, irrespective of stroke severity, although the independent contribution of depression on outcomes is still not fully understood.

Traditional Cognitive Behavioral Therapy

Cognitive behavioral therapy (CBT) is an effective treatment for common mood disorders. Studies have shown a beneficial effect of CBT for both the treatment and prevention of depression after stroke.^{3,4} There is also evidence suggesting that CBT may provide a more durable and lasting treatment effect than pharmacotherapy with selective serotonin reuptake inhibitors.⁵

Despite the promise of CBT, its role in routine clinical practice is limited. There are significant barriers to widespread use of CBT. First, access to experienced CBT practitioners is limited.⁶ Second, the time and travel requirements to complete a course of CBT, which may require 2-3 visits per week for 10-12 weeks, are onerous for many patients. This may be even more difficult for patients with mobility limitations, which are common after stroke. Third, the cost of CBT may be prohibitive, particularly if providers do not accept insurance.⁶ Finally, patients may be resistant to in-person CBT because of stigma or fear of sharing deeply personal feelings with a therapist.

Technology and CBT

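### The exploratory analyses lose information: Day-90 PHQ-9 is cut at the sample median, and the high/low engagement comparison states no baseline PHQ-9 term

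*Combined protocol and SAP*

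**What the plan says.** All of this is in the Analysis Plan of the combined protocol and SAP unless another section is named.

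- **Split on depressive symptoms.** "In an exploratory analysis, we will divide patients into two groups based on PHQ-9 at study completion". Subjects at or above the median are the high group and the rest the low group. "Healthcare outcomes, including modified Rankin scale, health related quality of life, and healthcare utilization will be compared across groups". A directional hypothesis is given: more symptoms go with worse function, lower quality of life and more utilization. No test is named.
- **Split on engagement.** The same paragraph continues: "We will also divide patients into groups based on their participation in the Joyable program". PHQ-9 score, quality of life and utilization are given as examples of outcomes to compare between high and low engagement. No engagement metric, cut, test or covariate is named.
- **What is available.** Entry PHQ-9 must lie between 5 and 19 (Inclusion Criteria) and is recorded for everyone. Activities completed, out of 42, is a primary outcome. EQ-5D is scheduled at baseline, Day 30 and Day 90 (Table 1).
- **A related analysis.** The plan will separately explore how baseline clinical and demographic factors relate to the number of activities completed. It does not carry this into the outcome comparison.

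**The concern.** The hypothesis on symptoms and outcome is monotone, and PHQ-9 is a graded score. Cutting it at the median treats a subject just above the cut like the most depressed subject in the sample, and unlike one just below it. In a 20-subject pilot that loss is noticeable.

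The engagement comparison has a different weakness. Subjects choose how much they engage, and entry scores can differ by up to 14 points (19 − 5). If more depressed subjects engage more, or less, a Day-90 difference between the groups partly reflects where they started. A pilot reader could take it as a sign of a dose-response when it is not one, or miss one that is there.

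**Working it through.** **Inputs from the document.** 20 subjects, single arm (Sample Size); α = 0.05 (Analysis Plan); entry PHQ-9 5 to 19; activities 0 to 42. PHQ-9 at study completion is read as the Day-90 value.

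**Assumptions (not in the document).** All correlations; Day-90 mean and SD; two-sided tests; 16 completers as a sensitivity case, since no dropout allowance is given.

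**The plan's own figures.** No power is stated for these analyses. Table 2 concerns the paired PHQ-9 comparison only. All 25 of its cells reproduce with n = 20 and a two-sided normal approximation: for a 3-point difference and SD 4, 3 × √20 / 4 = 3.354, and Φ(3.354 − 1.96) = 91.8%, printed as 92%. This is background; the point here does not touch Table 2.

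**Step 1. Information kept by a median cut.** For a roughly normal score the fraction kept is φ(0)² / 0.25 = 0.3989² / 0.25 = 0.637 (= 2/π). So 20 subjects count like about 20 × 0.637 = 12.7, and a true correlation r shrinks to about r × √0.637 = 0.80r.

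**Step 2. Power.** Simulation of a bivariate normal pair: Pearson test on the continuous score against a two-sample t-test after an equal split.

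| True r (assumed) | n = 20, continuous | n = 20, split | n = 16, continuous | n = 16, split |
|---|---|---|---|---|
| 0.1 | 7% | 6% | 7% | 6% |
| 0.2 | 13% | 10% | 11% | 9% |
| 0.3 | 25% | 17% | 21% | 14% |
| 0.4 | 43% | 28% | 35% | 22% |
| 0.5 | 64% | 42% | 53% | 34% |
| 0.6 | 84% | 60% | 73% | 49% |

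Repeat runs agree to about one percentage point. Step 1 serves as a check: the split at r = 0.5 should behave like the continuous score at 0.80 × 0.5 = 0.40, and it does (42% against 43%).

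Normality is not essential. With a skewed integer PHQ-9 (rounded gamma, assumed mean 6, SD 4.5), a five-level outcome (assumed shares 10/30/30/20/10%) and the median-or-above rule, Spearman against Mann-Whitney at n = 20 gives 37% v 23%, 55% v 36% and 75% v 53% at r = 0.4, 0.5 and 0.6.

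**Step 3. Engagement with no true effect.** Let r be the correlation of engagement with entry PHQ-9, and let entry PHQ-9 correlate 0.5 to 0.7 with Day-90 PHQ-9. With n = 20 split 10/10 and a t-test on Day-90 PHQ-9:

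| Correlation r | Type I error, unadjusted | With baseline PHQ-9 as covariate |
|---|---|---|
| 0 | 5% | 5% |
| ±0.15 | about 6% | 5% |
| ±0.3 | about 8 to 10.5% | 5% |

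Holding entry PHQ-9 to integers 5 to 19 and Day-90 PHQ-9 to 0 to 27 (resulting SD 4.28) leaves these rates essentially unchanged. The spurious difference is then 0.5 to 0.7 points at |r| = 0.15 and 1.0 to 1.4 points at |r| = 0.3.

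**The case against.** **The analyses are exploratory, and the median rule is fully stated.** True. The cut, the handling of ties and the hypothesis are all given, no power is claimed, and nothing contradicts itself. A reader might infer that the pilot's main conclusions are weakened. They are not: the primary outcomes do not use either split.

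**The power gain depends on correlations that nobody knows.** This stands. At r = 0.1 or 0.2 the gain is small (7% v 6%, 13% v 10%) and both methods have little power. The gain is material only from about 0.3 upward.

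**The plan does not rule out baseline adjustment.** Correct: it is silent, and it names no model at all. A reader might infer a decision to leave baseline PHQ-9 out, but the text does not show one. The planned look at baseline factors against activities completed could also reveal the troublesome correlation, if those factors include PHQ-9. Revealing it is not the same as adjusting for it.

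**The bias is small against the noise.** Also fair. The standard error of a 10 v 10 difference is 4.28 × √(1/10 + 1/10) = 1.9 points, so even 1.4 spurious points is less than one standard error. The case for adjusting is that it costs almost nothing.

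**The unnamed engagement metric.** The document offers several candidates: activities, "total amount of time spent interacting with the Joyable program", and "completion of the iCBT program, number of telephone/email based coaching interactions". A reader might infer that the metric will be picked after seeing results. Nothing in the document suggests that; it is missing detail that an analyst would fill sensibly.

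**Quality of life in Objective 2.** The objective is to "Quantify changes in depressive symptoms and quality of life in subjects pre- and post-program participation", and the plan states a pre/post comparison for PHQ-9 ("We will compare the PHQ-9 score from enrollment to day 90") but not for EQ-5D. A reader might infer that half the objective will go unanalysed. Objective 2 and the EQ-5D schedule in Table 1 already imply a paired change, so this is a wording gap only.

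**Conclusion.** The point holds as an efficiency and interpretability improvement to exploratory analyses. The median cut keeps about 64% of the information in a roughly normal score. At n = 20 it costs about 3 percentage points of power at r = 0.2, 8 at 0.3, and 15 to 24 at 0.4 to 0.6. The engagement comparison, if run without baseline PHQ-9, has a modestly raised false-positive rate: up to about 10.5% at |r| = 0.3, and none of that excess if engagement is unrelated to entry severity. Both sizes rest on assumed correlations, and the second also on reading the engagement comparison as an unadjusted contrast of Day-90 scores. The documents support nothing stronger about the validity of the pilot.

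**What to change.** Change the exploratory paragraph of the Analysis Plan:

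1. Relate continuous Day-90 PHQ-9 to mRS, EQ-5D and utilization by rank correlation or regression.
2. Regress Day-90 PHQ-9 on the number of activities completed (0 to 42), with baseline PHQ-9 as covariate; do the same for Day-90 EQ-5D with baseline EQ-5D. Activities completed is the natural metric: the protocol states "The primary outcomes will be the number of activities in the iCBT program completed by participants", and the count is in the data transfer listed under Data Confidentiality, where time spent is not named.
3. Report slopes with 95% CIs as associations, not treatment effects. Keep the grouped tables for description only.

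Minor wording note: for the quality-of-life half of Objective 2, name the EQ-5D score (index with its value set, or the 0 to 100 scale) and state that the baseline-to-Day-90 change will be given with a 95% CI.

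Cost: about one sentence per item, with no new data or visits. The price is an assumed linear or monotone relation and one degree of freedom per covariate, which is affordable at n = 20.
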